#### **6.10 Frequency and duration of follow up**

The follow-up schedule is described in Table 1, Section 0.

#### **6.11 Likely rate of loss to follow-up**

Assuming that 27% in the placebo group are free from TF 12 months after randomisation (estimated from placebo groups of the two trials with 40% active and 60% inactive disease [1, 4]), we have set a target sample size of 174 randomised participants. A study of this size will have 90% to detect a HR 0.5 at the 5% two-sided significance level, allowing for 10% loss-to-follow-up in the first 12 months.

There are no special features to minimise bias due to missing outcome data. Established methods will be used to maximise the proportion of participants for whom all outcome data are available and the proportion of participants who receive the intervention to which they were allocated. However, ANIU is a debilitating condition for patients who are affected and, subject to other comorbidities they experience, we expect participants to attend their follow-up visits as scheduled; these are set at the same frequency as required for usual care so extra research-only visits should be unnecessary.

#### **6.12 Expenses**

The schedule of follow-up visits has been designed to be the same as for usual care for a patient with ANIU. Therefore, it is not expected that participants will be reimbursed for travel expenses. Participants may be reimbursed for the cost of parking if a visit takes longer than a usual care visit as a direct result of research-specific procedures (i.e. assessments they would not have had if they were not taking part in the trial).

### **7. Statistical analyses**

#### **7.1 Plan of analysis**

The primary analysis of effectiveness will be restricted to data collected in the RCT. The data will be analysed according to intention to treat (ITT) and follow CONSORT reporting guidelines. Analyses will be adjusted for centre. The primary outcome, time from randomisation to first TF in the RCT, will be compared using survival methods, allowing for censoring of any participant who is lost to follow-up. Secondary outcomes up to the time of TF will be compared using a mixed linear or logistic regression model as appropriate, adjusted for baseline measures when available. These outcomes will be modelled jointly with the time to first TF. Changes in treatment effect with time will be assessed by adding a treatment x time interaction to the model and comparing models using a likelihood ratio test. Model fit will be assessed and alternative models and/or transformations (e.g. to induce normality) will be explored where appropriate. Frequencies of AEs will be described. Treatment differences will be reported with 95% CIs.

A secondary analysis will be carried out at the end of the OLE, including data from both the RCT and OLE, updating the primary analysis estimates. If additional first TFs are observed in the OLE, these will increase the precision of updated estimates of treatment effectiveness.

A further secondary analysis will include follow-up time after the first TF. A participant who experiences a first TF will restart adalimumab (repeating the TRI) for 16 weeks. If after 16 weeks the participant satisfies the criteria for being a responder, he/she will re-enter the trial treated with the opposite treatment to the one originally allocated (placebo if originally on intervention, or vice versa). Restarting treatment will become the time origin for the second period of follow-up. (This process can be repeated another time, in the event of a second TF, generating up to three discrete “disconnected” periods of follow-up. Follow-up will cease after a third TF.

The allocation group (and other important covariates) will be updated when “study” treatment (intervention or placebo) is restarted. We will analyse multiple periods of treatment exposure within participants with survival models. The primary analysis, i.e. time to first TF will be unbiased. Analyses of subsequent follow-up periods must be considered to be non-randomised, and potentially biased, since participants’ characteristics are likely to predict TF. Therefore, if adalimumab is effective, second and third follow-up periods will not be distributed in a balanced way across the original randomly assigned groups and it will be necessary to consider important covariates. Nevertheless, switches will provide a within-subject comparison of survival free from TF between intervention and placebo.

A detailed analysis plan will be prepared.

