Cost-effectiveness analysis:	The main outcome measure for the economic evaluation will be quality adjusted life years (QALYs), estimated using the EuroQol EQ-5D 5L, administered at every visit. Valuations derived from published UK population tariffs will be assigned. The mean number of QALYs per group and incremental QALYs will be calculated.
Sample size:	Hazard ratios (HRs) in 2 trials of adalimumab to treat active and inactive ANIU were 0.50 and 0.57 respectively [1, 4]. The TRI design should improve effectiveness and we have set a target HR of 0.5. Assuming that 27% in the placebo group survive free from TF at 12m (estimated from placebo groups of the 2 trials with 40:60 active: inactive disease), 174 participants will allow a HR=0.5 (27% vs 52% survival free from TF at 12 months) to be detected with 90% power and 5% 2-tailed significance, with <=10% loss to follow-up.
Project timetable:	58 months comprising 7 months set-up; 34 months recruitment (which includes 4 months TRI and 4 months randomising last recruited participants at end of TRI); 14 months follow-up in OLE 3 months data for final analyses and reporting. (Ongoing data checks will be completed.)
Expertise in team:	The multidisciplinary team includes ophthalmologists who treat ANIU, a patient with ANIU, an imaging expert, clinical trials researchers with expertise conducting ophthalmic trials and a health economist.

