## 1.2 Plain English summary

Autoimmune uveitis is a term for several rare eye diseases in which the body's own immune system causes sight-threatening damage to the light sensitive retina at the back of the eye. Uveitis causes sight loss from inflammation inside the eye, damage to blood vessels in the

retina or leakage of fluid into the central, most sensitive area of the retina. Two in 10,000 people are at risk of serious sight loss from uveitis. Usual treatment for autoimmune uveitis involves low dose steroids and one or two other drugs to reduce inflammation. Unfortunately, many patients do not respond to or tolerate usual treatment, or they need high dose steroids to control the uveitis. Long term high dose steroids increase the risk of heart attack, stroke, and infection and affect physical and mental health. Adalimumab is a drug that targets chemicals released by inflamed tissue, neutralising their damage to the body. It was first approved in Europe to treat uveitis in 2016.

Two recent studies suggest fortnightly adalimumab is, on average, an effective way to treat uveitis in some patients. However, drugs like adalimumab can have serious side effects and more evidence is required to identify which patients with uveitis benefit the most from adalimumab, both with respect to their vision and quality of life, including treatment side effects. In 2017, NICE recommended that it should be used in the National Health Service (NHS) but only for a minority of patients with uveitis. Several very similar (biosimilar) drugs are now available, reducing the cost of treatment, and ophthalmologists believe that many more patients could benefit but have no way to identify those most likely to benefit. This study is designed to evaluate one of these biosimilar drugs, now being purchased by the UK NHS for usual care.

This study aims, first, to identify patients who are most likely to benefit from adalimumab. All eligible patients who consent will be given adalimumab for a 16-week trial period, if necessary in combination with low dose of steroids; these patients will include those with impaired vision due to uveitis, requiring high dose steroids to bring the disease under control, and those with better vision but who require high dose steroids to keep the uveitis under control. Over the 16 weeks, doctors will aim to reduce the steroid dose to a low level that should not cause side effects.

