## 5.9 Sample size justification

We hypothesise that participants randomised to receive adalimumab will have a lower risk of TF than those allocated to receive placebo. The sample size has been chosen to test this hypothesis. In estimating the sample size, we have considered the results observed in previous studies; hazard ratios (HRs) for time to first TF in two previous trials of adalimumab (in patients with active and inactive ANIU, respectively) were 0.50 and 0.57 [1, 4]. As our study will only randomise participants who are found to respond to treatment in the TRI phase, we anticipate that we will observe a greater benefit than in these trials, which included both responders and non-responders. Therefore, we have set the target HR at 0.5. Assuming that 27% in the placebo group survive free from TF 12 months after randomisation (estimated from placebo groups of the two trials with 40% active and 60% inactive disease), we have set a target sample size of 174 randomised participants. A study of this size will have 90% power to detect a HR 0.5 at a 5% two-sided significance level, allowing for 10% loss-to-follow-up in the first 12 months.

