## 6. Trial methods

### 6.1 Description of randomisation

Eligibility will be checked, and consent obtained to the whole study at the beginning of the TRI, with both being confirmed at the 16-week visit when responder status has been ascertained and eligibility for the trial has been confirmed. Randomisation will be carried out at this visit so that the appropriate IMP can be prescribed at the same time. Randomisation will be performed by a member of the local research team on the delegation log who is authorised to do so using a secure internet-based randomisation system ensuring allocation concealment. Participants will be allocated in a 1:1 ratio to either adalimumab or placebo.

The random allocations will be computer-generated by a statistician in the trials unit in blocks of varying size (unknown to trial personnel) and stratified by centre, before the trial starts to recruit. The allocations will be embedded in the trial database and concealed from all clinical and research personnel until a participant has been recruited. Key data to characterise a participant's current clinical status at will be collected at the time of randomisation.

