## **7.2 Subgroup analyses**

No subgroup analyses are planned.

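### The primary analysis of time to first treatment failure names centre as its only adjustment; adding active or controlled disease at run-in entry, already recorded for everyone, would protect power

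*Protocol*

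**What the plan says.** Section 7.1 restricts the primary analysis to the randomised phase, analyses it by intention to treat with survival methods, and says "Analyses will be adjusted for centre". It mentions adjustment for baseline measures only for the secondary outcomes. Section 6.1 generates allocations "in blocks of varying size (unknown to trial personnel) and stratified by centre", so the stated adjustment matches the only stratification factor.

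Active or controlled disease appears elsewhere as a planning variable:

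- Inclusion criterion 2 (section 5.6.1) admits a participant under either active or controlled disease, so the status is known for everyone before the run-in.
- Section 5.9 takes the 27% placebo rate as "estimated from placebo groups of the two trials with 40% active and 60% inactive disease".
- Table 2 projects recruitment separately by status, with totals of 285 inactive and 129 active.

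Section 7.2 adds "No subgroup analyses are planned". Sections 5.5 and 7.1 promise a detailed analysis plan.

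**The concern.** When a covariate that predicts failure is left out of a proportional hazards model, the treatment hazard ratio moves toward 1 and power falls, even with perfect randomisation. The planning rate is a weighted average over the two disease groups, which suggests that the planners expected entry status to matter for TF. Allocation is stratified by centre alone, so a chance imbalance in entry status between arms would not be corrected by the stated model.

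At stake is some of the planned 90% power, and a headline hazard ratio that depends partly on the mix of patients recruited. That mix is uncertain within the protocol itself: 40% active in section 5.9, against 129/414 = 31% active among projected run-in entrants in Table 2.

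**Working it through.** **Inputs.** Section 5.9: "A study of this size will have 90% power to detect a HR 0.5 at a 5% two-sided significance level", 174 randomised, 10% loss in the first 12 months, 40% active. Section 1.1: "27% vs 52% survival free from TF at 12 months".

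**Reproducing the plan's figure.** Freedman's formula gives events d = ((1 + HR)/(1 − HR))² × (1.96 + 1.2816)² = 9 × 10.51 = 94.6, so 95. The mean event probability is (0.73 + 0.48)/2 = 0.605. Then 95/0.605 = 157.02, so 158 patients. Dividing by 0.9 gives 176; multiplying by 1.1 gives 174. The stated size reproduces. At 174, expected events are 174 × 0.9 × 0.605 = 94.7, and power is Φ(√94.7 × 0.5/1.5 − 1.96) = 90.1%.

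**Effect of omitting entry status: large-sample approximation.** The protocol gives no TF rates by status, so these are assumed. Let Sa be the placebo TF-free rate at 12 months in the active group. The controlled rate must then be Sc = (0.27 − 0.4 × Sa)/0.6 to keep the 27% average. With exponential hazards, the multiplier for active status is ln(Sa)/ln(Sc). For example, Sa = 0.12 gives Sc = 0.37 and a multiplier of 2.120/0.994 = 2.13. The true hazard ratio within each status is 0.5. The hazard ratio without status comes from a Cox fit to 1,000,000 simulated participants followed for 12 months. Power is Φ(√d × (1 − HR)/(1 + HR) − 1.96).

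| Sa / Sc | Multiplier | HR without status | Power without | Power with |
|---|---|---|---|---|
| 22% / 30% | 1.27 | 0.50 | 89.9% | 90.1% |
| 17% / 34% | 1.63 | 0.51 | 88.9% | 90.2% |
| 12% / 37% | 2.13 | 0.52 | 86.7% | 90.4% |
| 7% / 40% | 2.93 | 0.54 | 83.3% | 90.8% |

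Third row as an example: d = 96.0, √96.0 × 0.478/1.522 − 1.96 = 1.12, and Φ(1.12) = 0.87.

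**Simulated trials.** With 2,000 trials per setting (174 randomised, true HR 0.5, 40% active, 12 months' follow-up, 10% annual loss):

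- Multiplier 1.5 or below: no loss.
- Multiplier 2: HR 0.52 without status (power 91%) and 0.50 with it (93%), a loss of 2 points.
- Multiplier 3: HR 0.54 without status (88%) and 0.50 with it (94%), a loss of 6 points.

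A separate simulation at the same planning values gave 0.51 (92% against 94%) at 2 and 0.55 (86% against 91%) at 3. It found no loss from adjusting at multipliers of 1 to 1.5.

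**Taken together.** At 2 the loss is about 1 to 4 points. At 3 it is mostly 6 to 7 points, with 5 in one simulation and 7.5 in the approximation.

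**The case against.** The strongest reply is that nothing in the plan is wrong. Adjusting for the stratification factor follows the design, and the randomised test is valid without entry status. The movement toward 1 arises because a hazard ratio averaged over status differs from one within status, and is not confounding. All of this stands.

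The prognostic premise is also not in the protocol. To be randomised, every participant must meet the responder criteria of section 6.3.1: no active disease, on low-dose prednisolone for the uveitis, after 16 weeks of adalimumab. Entry status is measured before that filter and may carry little weight after it. A multiplier of 3 implies placebo TF-free rates of about 7% in the active group and 41% in the controlled group, which is a wide gap among responders. This also stands, and it is why the loss is given as a range.

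Finally, the statistical analysis plan is not shown and may already add the covariate. If it does, the point is closed.

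Two stronger readings are tempting. The first is that the trial cannot meet its own first aim, because the lay summary (section 1.2) says "This study aims, first, to identify patients who are most likely to benefit from adalimumab". The sentences after it describe doing this through the run-in, and section 5.1 likewise uses short-term response to personalise treatment. Section 4 tests the effectiveness hypothesis first and lists patient factors last, as objective D, which concerns associations with response and with TF. The second is that section 7.2 must be replaced by a treatment-by-status interaction. With about 95 events split 40:60, the standard error of the log ratio of hazard ratios is √(4/38 + 4/57) = 0.42. A test would have about 6% power to separate the 0.50 and 0.57 cited in section 5.9. Planning no subgroups is a defensible choice at that size.

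**Conclusion.** The point holds as a suggestion for efficiency. Section 7.1 names centre alone for the primary outcome, while a covariate that weights the planning rate is already recorded for everyone. The primary test remains valid and the target of 174 reproduces.

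The benefit of adjusting depends on an unknown quantity, the TF hazard in active relative to controlled entrants after the responder filter. It is negligible at a multiplier of 1.5 or less, about 1 to 4 power points at 2, and about 6 to 7 at 3. Whether unadjusted power at 2 falls below 90% depends on the method: the approximation puts it at 87%, the simulations at 91% to 92%.

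These figures assume exponential hazards, a common hazard ratio of 0.5 in both groups, 40% active and 12 months of follow-up. They do not model centre effects or the planned 12 to 170 weeks of follow-up. With 31% active the approximation gives slightly smaller losses: power of 87.9% against 90.3% at a multiplier of 1.95. The finding does not extend to bias, to failure of a stated aim, or to a need for subgroup analysis.

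**What to change.** Before database lock, prespecify in section 7.1, and carry into the statistical analysis plan, that the primary model for time to first TF is adjusted for centre and for active or controlled uveitis at run-in entry. Section 7.2 can stay as it is.

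The cost is wording. The data are already collected under inclusion criterion 2, and the model gains one parameter. In the simulations, adjusting lost no power when status had little or no effect. The small downside is that the reported hazard ratio is then conditional on entry status, which the report should say. Timing matters because a covariate chosen after the results are known would be post hoc.

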## **5.8 Primary and secondary outcomes**

### ***5.8.1 Primary outcome***

The primary outcome is time to the first treatment failure (TF), for a participant, i.e. TF may occur in either eye and may be triggered by incident ANIU in an eye that did not previously have ANIU. TF is defined as a composite of standard criteria reflecting clinical decision-making, including visual acuity and clinical signs of active inflammation which have been used successfully in other ANIU trials [1, 4, 58].

Our definition of TF will modify the composite endpoint used in the VISUAL trials [1,2] by: (i) excluding isolated anterior uveitis as a TF event (it can be treated effectively and safely with low dose, low frequency topical CS); and (ii) including a clinically important deterioration in CMO as a TF event [11], because it is an ANIU complication causing visual loss in a third of patients [59] which has often studied as a TF event in other trials of ANIU.

Participants will be assessed for TF at each visit after randomisation.

Any of the following criteria in one or both eyes, where applicable, will constitute TF:

- i.  $\geq 15$  letter decrease in best corrected visual acuity (BCVA), compared to BCVA measured by an optometrist masked to treatment allocation at the 16 week TRI visit;
- ii. new active inflammatory chorioretinal lesions (masked review of fundus colour and autofluorescence images by clinician during the RCT; unmasked during the OLE);
- iii.  $>20\%$  increase in central macular thickness (CMT), compared to CMT at the 16 week TRI timepoint (CMT is a parameter that is measured by an automated algorithm when doing optical coherence tomography (OCT));
- iv. onset or worsening of retinal vasculitis (masked clinician assessment of fundus fluorescein angiogram during the RCT; unmasked during the OLE);
- v. 2 step worsening of vitreous haze compared to score at the 16-week TRI visit (masked clinician assessment during the RCT; unmasked during the OLE);
- vi. prescription by a masked clinician of  $>5\text{mg/day}$  oral prednisolone to maintain uveitis remission (i.e. to avert relapse before any of the above criteria for manifest active disease (i-v) during the RCT; unmasked during the OLE).

Prescription of  $>5\text{mg/day}$  oral prednisolone for a co-morbidity (e.g. rheumatic disease) but with none of i-v being present does not constitute TF.

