### 5.8.2 Secondary outcomes

Secondary outcomes will include:

- a) Individual TF components, assessed at each trial visit;
- b) Retinal morphology (OCT; macular and retinal nerve fibre layer), assessed at each trial visit;
- c) AEs, assessed at each trial visit;
- d) HRQoL measured using the EQ-5D-5L questionnaire [3][7] at the start of TRI, at 16 weeks immediately before randomisation, then 12-weekly after randomization up to week 48 and 16-weekly thereafter;
- e) Patient-reported symptoms of side-effects at the start of TRI, at 16 weeks (immediately before randomisation), then at each trial visit after randomisation and at any interim attendance prompted by an AE;
- f) Patient-reported visual function [2], at the start of TRI, at 16 weeks immediately before randomisation, 12-weekly up to week 48 and 16 weekly thereafter;
- g) Best corrected visual acuity (BCVA) assessed at each trial visit;
- h) Employment status at the start of TRI, at 16 weeks immediately before randomisation, 12-weekly up to week 48 and 16 weekly thereafter;
- i) Resource use at the start of TRI, at 16 weeks immediately before randomisation, and every 12 weeks (up to week 48) or 16 weeks (after week 48) during follow-up after randomisation.

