### 10.2 Risks and anticipated benefits

For patients who are not eligible for adalimumab under NICE guidance, the main benefit of participation is the provision of adalimumab for the period of the TRI and, if classified as a responder conditional randomization, subsequently in the RCT. For patients who are eligible for adalimumab under NICE guidance, the main benefit will be knowing more accurately whether they are responders or not and further contributing to the UK cohort of safety and tolerability (which is being maintained for the benefit of all patients being treated with adalimumab).

For patients who are eligible for adalimumab under NICE guidance, the main risk of participation is potential permanent damage from ANIU if a participant is allocated to placebo after being classified as a responder. However, the risk is low as patients with the highest risk of deterioration (e.g. patients with Behcet's disease) will not be included in the study and follow-up visits are frequent enough that treatment failure should be identified before any permanent damage occurs. For all participants, there is also a potential risk of a serious adverse reaction from adalimumab, although such events are rare.

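### The rule that secondary outcomes are analysed up to TF, jointly with time to TF, is circular for the TF components and leaves vision and patient-reported outcomes with no stated comparison by arm after TF

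*Protocol*

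**What the plan says.** Protocol section 7.1 says that the analysis follows intention to treat. For secondary outcomes it fixes a data cut and a model, "Secondary outcomes up to the time of TF will be compared using a mixed linear or logistic regression model as appropriate", and adds: "These outcomes will be modelled jointly with the time to first TF".

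Section 5.8.2 lists as outcome (a) "Individual TF components, assessed at each trial visit". The list also includes retinal morphology, EQ-5D-5L, patient-reported visual function (VCM1) and BCVA. Section 5.8.1 defines the composite: "Any of the following criteria in one or both eyes, where applicable, will constitute TF". The same section exempts criteria met within 14 days of intraocular surgery.

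Objective B in section 4 promises between-group differences in these outcomes and names the separate components of TF. No other method for the components is given.

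For time after a first TF, section 7.1 plans survival models of repeated treatment periods, and calls those periods non-randomised and potentially biased. It describes no comparison of vision or questionnaire scores after TF.

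Two items sit outside the cut as written. Adverse event frequencies are described (7.1), and QALYs and costs are calculated per arm (7.5).

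**The concern.** There are two separate problems.

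First, a rule that suits a continuous measurement is applied to outcomes that define the truncating event. A component has no history before TF, because its first appearance is the TF. A repeated-measures model of it, linked to time to TF, has no clear interpretation. Objective B then has no usable analysis of which components adalimumab prevents.

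Second, stopping the vision and patient-reported comparisons at TF conditions them on something that treatment affects. If adalimumab works, placebo participants leave these comparisons earlier and in greater numbers. What is estimated is the difference while participants are free of TF. Visual or quality-of-life loss that arises after TF is counted in no stated clinical comparison by randomised arm. Section 10.2 discusses permanent damage as the main risk of placebo allocation for patients eligible for the drug under NICE guidance, and reasons that "follow-up visits are frequent enough that treatment failure should be identified before any permanent damage occurs". A comparison by arm after TF would be relevant evidence on that point, and none is planned.

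**Working it through.** **Inputs.** Placebo TF-free at 12 months is 27% (section 5.9: "Assuming that 27% in the placebo group survive free from TF 12 months after randomisation"). The arms compared are "27% vs 52% survival free from TF at 12 months" (section 1.1). The hazard ratio is 0.5, with 90% power, 5% two-sided, 10% loss and 174 randomised 1:1, so 87 per arm (sections 5.9 and 6.1).

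**The plan's own figure.** 0.27^0.5 = 0.5196, which agrees with the stated 52%. Freedman events = (1.960 + 1.282)² × ((1 + 0.5)/(1 − 0.5))² = 10.51 × 9 = 94.6, so 95. The mean event probability is 1 − (0.27 + 0.52)/2 = 0.605, and 95/0.605 = 157.0, rounded up to 158. Allowing for loss, 158/0.9 = 175.6 or 158 × 1.1 = 173.8. The stated 174 reproduces, and 174 × 0.9 × 0.605 = 94.7 events gives 90.1% power. The planning assumptions are coherent and can be used to size the cut.

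**Size of the cut.** Assume exponential times to TF. The placebo hazard is −ln(0.27)/52 = 0.0252 per week, and the adalimumab hazard is half that. TF-free share at week t = exp(−hazard × t), before any other loss and for participants followed that long:

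| Week | TF-free, placebo | TF-free, adalimumab | TF by then, placebo vs adalimumab |
|---|---|---|---|
| 24 | 55% | 74% | 45% vs 26% |
| 48 | 30% | 55% | 70% vs 45% |
| 96 | 9% | 30% | 91% vs 70% |

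At week 48 about 26 of 87 placebo and 47 of 87 adalimumab participants would still be contributing, a gap of 25 percentage points. The share of the first 52 weeks that lies before TF is (1 − 0.27)/1.309 = 56% on placebo and (1 − 0.52)/0.655 = 73% on adalimumab.

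**The components.** No arithmetic is needed. Take any criterion from i to vi at a visit after randomisation. If it is present and not within the surgery window, the participant has had TF. So at every earlier visit the indicator is zero in both arms, whatever the treatment.
- If the TF visit is excluded, the outcome has no variation.
- If the TF visit is included, the only non-zero value is the event that already forms the survival part of the joint model.

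BCVA and central macular thickness are affected more mildly. Before TF they cannot show a fall of 15 letters or more, or a rise above 20%, because either is a TF.

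**The case against.** The case for the plan as written is substantial.

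- Joint modelling is a recognised way to handle a continuous outcome cut off by a related event. That stands, and the model should stay for those outcomes.
- The cut has a reason. After TF both arms restart open-label adalimumab, and responders then switch allocation (section 5.1), so later differences by arm mix treatments. That also stands, and it is why an all-visits comparison should support the joint model and not lead.
- Post-TF data will be incomplete. Sections 5.1 and 5.7 say that repeat run-in non-responders leave the trial, while section 6.9 asks those who stop treatment to keep attending. If the 0.50 response rate in the Table 2 footnote also held for repeat run-ins (an assumption), TF by week 32 would be 55% vs 33%, and about half of these, 28% vs 17%, would have left by week 48. The visit clock also restarts at the response assessment (Table 1 notes), and RCT follow-up can be as short as 12 weeks.
- The wording may include the TF visit, at which all follow-up assessments are collected (section 6.3). Loss present at that visit would then be retained and only later loss dropped. The text does not settle this.
- Detail may be left to an analysis plan, which is not shown. But section 7.1 itself fixes both the cut and the joint model, and a plan that follows it inherits both.

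A reader might infer more than the documents support. Not every secondary outcome is cut at TF: adverse events and QALYs are not stated to be, so quality-of-life loss after TF can still reach the economic results. Nor can the gap in TF be converted into letters of vision lost. The documents give no visual loss per TF, and section 10.2 expects none that is permanent. That section is also a risk rationale, not an objective that the trial undertook to test.

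**Conclusion.** The point holds in a limited form. For outcome (a) the stated method is circular; this follows from the definitions alone, and the surgery exception does not change it. For BCVA, VCM1, retinal morphology and EQ-5D as a clinical outcome, the only stated between-group comparison ends at an event that treatment affects, so it does not estimate the effect over all follow-up that the intention-to-treat statement suggests. The imbalance is about 70% vs 45% by week 48. It rests on 27% TF-free at 12 months, a hazard ratio of 0.5 and an exponential shape. The bias in any particular outcome cannot be sized from the documents. The primary outcome is not affected. The change should be made, but it does not put the trial's main conclusion at risk.

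**What to change.** 1. **TF components.** Analyse each by cause-specific hazard and cumulative incidence by randomised arm at first TF, with the other components as competing events. Add a rule for components that occur together at the same visit.
2. **Continuous outcomes.** Keep the joint model, state that it targets the course up to TF, and include the TF visit.
3. **Supportive analysis.** Compare BCVA, VCM1, EQ-5D and central macular thickness by randomised arm, using all available visits regardless of TF and timed from randomisation. Report how many participants in each arm contribute after TF, and why others do not.
4. **Scope.** State that adverse events and QALYs are not cut at TF, if that is the intention. Reconcile sections 5.1 and 5.7 with section 6.9 on whether repeat run-in non-responders continue to attend.

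The cost is wording and analysis time; no new assessments are needed. The downside lies in item 3. It compares starting strategies, is diluted by adalimumab use and switching after TF, and rests on incomplete data because some participants exit and the visit clock restarts.
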